**Table 3.7.3-2 Sparse Sampling Schedule Trial Days and Activities**

|   |   |
|---|---|
| █ | 
 
• Draw blood for CYP2D6 pharmacogenomics.
 
• Randomize to aripiprazole 2M LAI 960 mg or aripiprazole IM depot 400 mg.
 
• Draw a PK blood sample within 2 hours prior to dosing.
 
• Assessment and confirmation by the investigator that the injection site is appropriate 30 minutes prior to IMP injection.
 
• Have subjects complete a VAS of the level of perceived pain at the injection site approximately 30 minutes prior to IMP injection.
 
• Administer IMP (aripiprazole IM depot 400 mg or aripiprazole 2M LAI 960 mg).
 
 
Postdose:
 
 
• Have subjects complete a VAS of the level of perceived pain at the injection site 1 hour (<math>\pm</math> 15 minutes) postdose.
 
• Assessment of the injection site by the investigator completed approximately 1 hour (<math>\pm</math> 15 minutes) postdose.
 
• Draw a PK blood sample at 4, 8, and 12 hours postdose.
 
 |
|   | Day 8 <math>\pm</math> 2 days (outpatient, all subjects)   |
|   | 
 
• Document birth control methods.
 
• Record concomitant medications and review for prohibited or restricted medications.
 
• Record adjustment of current oral antipsychotic, mood stabilizer, or antidepressant therapy.
 
• Assess and record AEs.
 
• Subjects assigned to aripiprazole 2M LAI 960 mg will discontinue taking 10 to 20 mg oral aripiprazole and/or current oral antipsychotic (as applicable) until the end of the trial. Subjects may resume treatment on their previous oral non-aripiprazole antipsychotic after Day 28, if there is evidence of clinical deterioration based on the judgment of the investigator.
 
• Take vital signs (systolic and diastolic blood pressure, heart rate, and body temperature).
 
• Administer the Since Last Visit version of the C-SSRS.
 
• Assess EPS (SAS, AIMS, and BARS).
 
• Draw a PK blood sample between 8 AM and 2 PM.
 
   |
|   | Days 15 and 22 <math>\pm</math> 2 days (outpatient, all subjects)  |
|   | 
 
• Document birth control methods.
 
• Record concomitant medications and review for prohibited or restricted medications.
 
• Record adjustment of current oral antipsychotic, mood stabilizer, or antidepressant therapy.
 
• Assess and record AEs.
 
• Perform a physical examination (Day 15 only).
 
• Take vital signs (systolic and diastolic blood pressure, heart rate, and body temperature).
 
• Administer the Since Last Visit version of the C-SSRS.
 
• Administer a 12-lead safety ECG in triplicate (5 minutes apart; Day 15 only).
 
   |

Protocol 031-201-00181

**Table 3.7.3-2 Sparse Sampling Schedule Trial Days and Activities**

- Assess EPS (SAS, AIMS, and BARS).
- Draw a PK blood sample between 8 AM and 2 PM.
- Discharge subjects housed in the clinical unit for an optional stay after completing all activities (Day 22).

**Day 29 ± 2 days (outpatient, all subjects)**

- Document birth control methods.
- Record concomitant medications and review for prohibited or restricted medications.
- Record adjustment of current oral antipsychotic, mood stabilizer, or antidepressant therapy.
- Assess and record AEs.
- Perform a urine pregnancy test (FOCBP only).
- Perform a physical examination.
- Measure weight.
- Take vital signs (systolic and diastolic blood pressure, heart rate, and body temperature).
- Administer a 12-lead safety ECG in triplicate (5 minutes apart).
- Collect clinical laboratory samples for hematology, clinical chemistry, prolactin assessment, and urinalysis.
- Administer the Since Last Visit version of the C-SSRS (predose).
- Assess EPS (SAS, AIMS, and BARS) (predose).
- Administer the PANSS (schizophrenia subjects only).
- Administer CGI-S scale and SWN-S (all subjects).
- Administer the MADRS, YMRS, and CGI-BP (bipolar subjects only).

**For subjects who receive aripiprazole 2M LAI 960 mg:**

- Draw a PK blood sample between 8 AM and 2 PM.

**For subjects who receive aripiprazole IM depot 400 mg:****Predose:**

- Draw a PK blood sample within 2 hours prior to dosing.
- Assessment and confirmation by the investigator that the injection site is appropriate 30 minutes prior to IMP injection.
- Have subjects complete a VAS of the level of perceived pain at the injection site approximately 30 minutes prior to IMP injection.
- Administer IMP.

**Postdose:**

- Have subjects complete a VAS of the level of perceived pain at the injection site approximately 1 hour (± 15 minutes) postdose.
- Assessment of the injection site by the investigator completed approximately 1 hour (± 15 minutes) postdose.

Protocol 031-201-00181

**Table 3.7.3-2 Sparse Sampling Schedule Trial Days and Activities**

| Days 36, 43, and 50 ± 2 days (outpatient, subjects receiving aripiprazole 2M LAI 960 mg)   |  |
|---|--|
| 
 
• Document birth control methods.
 
• Record concomitant medications and review for prohibited or restricted medications.
 
• Record adjustment of current oral antipsychotic, mood stabilizer, or antidepressant therapy.
 
• Assess and record AEs.
 
• Take vital signs (systolic and diastolic blood pressure, heart rate, and body temperature).
 
• Administer the Since Last Visit version of the C-SSRS.
 
• Draw a PK blood sample between 8 AM and 2 PM.
 
  |  |
| Day 57 ± 2 days (outpatient, all subjects)   |  |
| 
Predose:
 
 
• Document birth control methods.
 
• Record concomitant medications and review for prohibited or restricted medications.
 
• Record adjustment of current oral antipsychotic, mood stabilizer, or antidepressant therapy.
 
• Assess and record AEs.
 
• Perform a urine pregnancy test (FOCBP only).
 
• Measure weight.
 
• Take vital signs (systolic and diastolic blood pressure, heart rate, and body temperature).
 
• Administer a 12-lead safety ECG in triplicate (5 minutes apart).
 
• Administer the Since Last Visit version of the C-SSRS.
 
• Assess EPS (SAS, AIMS, and BARS).
 
• Administer the PANSS (schizophrenia subjects only).
 
• Administer CGI-S scale, CGI-I scale, and SWN-S (all subjects).
 
• Administer the MADRS, YMRS, and CGI-BP (bipolar subjects only).
 
• Draw a PK blood sample (within 2 hours prior to dosing).
 
• Assessment and confirmation by the investigator that the injection site is appropriate 30 minutes prior to IMP injection.
 
• Have subjects complete a VAS of the level of perceived pain at the injection site completed approximately 30 minutes prior to IMP injection.
 
• Administer IMP.
 
 |  |
| 
Postdose:
 
 
• Have subjects complete a VAS of the level of perceived pain at the injection site approximately 1 hour (± 15 minutes) postdose.
 
• Assessment of the injection site by the investigator completed approximately 1 hour (± 15 minutes) postdose.
 
  |  |
| Day 85 ± 2 days (outpatient, all subjects)   |  |
| 
 
• Document birth control methods.
 
   |  |

Protocol 031-201-00181

**Table 3.7.3-2 Sparse Sampling Schedule Trial Days and Activities**

- Record concomitant medications and review for prohibited or restricted medications.
- Record adjustment of current oral antipsychotic, mood stabilizer, or antidepressant therapy.
- Assess and record AEs.
- Perform a urine pregnancy test (FOCBP only).
- Measure weight. Take vital signs (systolic and diastolic blood pressure, heart rate, and body temperature).
- Administer the Since Last Visit version of the C-SSRS (predose).
- Assess EPS (SAS, AIMS, and BARS) (predose).

**For subjects who receive aripiprazole 2M LAI 960 mg:**

- Draw a PK blood sample between 8 AM and 2 PM.

**For subjects who receive aripiprazole IM depot 400 mg:****Predose:**

- Draw a PK blood sample (within 2 hours prior to dosing).
- Assessment and confirmation by the investigator that the injection site is appropriate 30 minutes prior to IMP injection.
- Have subjects complete a VAS of the level of perceived pain at the injection site approximately 30 minutes prior to IMP injection.
- Administer IMP.

**Postdose:**

- Have subjects complete a VAS of the level of perceived pain at the injection site approximately 1 hour ( $\pm$  15 minutes) postdose.
- Assessment of the injection site by the investigator completed approximately 1 hour ( $\pm$  15 minutes) postdose.

**Day 113  $\pm$  2 days (outpatient, all subjects)****Predose:**

- Document birth control methods.
- Record concomitant medications and review for prohibited or restricted medications.
- Record adjustment of current oral antipsychotic, mood stabilizer, or antidepressant therapy.
- Assess and record AEs.
- Perform a urine pregnancy test (FOCBP only).
- Perform a physical examination.
- Measure weight.
- Take vital signs (systolic and diastolic blood pressure, heart rate, and body temperature).
- Administer a 12-lead safety ECG in triplicate (5 minutes apart).
- Administer the Since Last Visit version of the C-SSRS.

Protocol 031-201-00181

**Table 3.7.3-2 Sparse Sampling Schedule Trial Days and Activities**

- Assess EPS (SAS, AIMS, and BARS).
- Administer the PANSS (schizophrenia subjects only).
- Administer CGI-S scale and SWN-S (all subjects).
- Administer the MADRS, YMRS, and CGI-BP (bipolar subjects only). Draw a PK blood sample within 2 hours prior to dosing.
- Assessment and confirmation by the investigator that the injection site is appropriate 30 minutes prior to IMP injection.
- Have subjects complete a VAS of the level of perceived pain at the injection site approximately 30 minutes prior to IMP injection.
- Administer IMP (aripiprazole IM depot 400 mg or aripiprazole 2M LAI 960 mg).

**Postdose:**

- Have subjects complete a VAS of the level of perceived pain at the injection site 1 hour ( $\pm$  15 minutes) postdose.
- Assessment of the injection site by the investigator completed approximately 1 hour ( $\pm$  15 minutes) postdose.

**Day 141  $\pm$  2 days (outpatient, all subjects)**

- Document birth control methods.
- Record concomitant medications and review for prohibited or restricted medications.
- Record adjustment of current oral antipsychotic, mood stabilizer, or antidepressant therapy.
- Assess and record AEs.
- Perform a urine pregnancy test (FOCBP only).
- Measure weight.
- Take vital signs (systolic and diastolic blood pressure, heart rate, and body temperature).
- Administer the Since Last Visit version of the C-SSRS (predose).
- Assess EPS (SAS, AIMS, and BARS) (predose).

**For subjects who receive aripiprazole 2M LAI 960 mg:**

- Draw a PK blood sample between 8 AM and 2 PM.

**For subjects who receive aripiprazole IM depot 400 mg:****Predose:**

- Draw a PK blood sample (within 2 hours prior to dosing).
- Assessment and confirmation by the investigator that the injection site is appropriate 30 minutes prior to IMP injection.
- Have subjects complete a VAS of the level of perceived pain at the injection site approximately 30 minutes prior to IMP injection.
- Administer IMP.

Protocol 031-201-00181

**Table 3.7.3-2 Sparse Sampling Schedule Trial Days and Activities****Postdose:**

- Have subjects complete a VAS of the level of perceived pain at the injection site approximately 1 hour ( $\pm$  15 minutes) postdose.
- Assessment of the injection site by the investigator completed approximately 1 hour ( $\pm$  15 minutes) postdose.

**Day 169  $\pm$  2 days (outpatient, all subjects)****Predose:**

- Document birth control methods.
- Record concomitant medications and review for prohibited or restricted medications.
- Record adjustment of current oral antipsychotic, mood stabilizer, or antidepressant therapy.
- Assess and record AEs.
- Perform a urine pregnancy test (FOCBP only).
- Measure weight.
- Take vital signs (systolic and diastolic blood pressure, heart rate, and body temperature).
- Administer the Since Last Visit version of the C-SSRS.
- Assess EPS (SAS, AIMS, and BARS).
- Administer the PANSS (schizophrenia subjects only).
- Administer CGI-S scale and SWN-S (all subjects).
- Administer the MADRS, YMRS, and CGI-BP (bipolar subjects only).
- Draw a PK blood sample within 2 hours prior to dosing.
- Assessment and confirmation by the investigator that the injection site is appropriate 30 minutes prior to IMP injection.
- Have subjects complete a VAS of the level of perceived pain at the injection site approximately 30 minutes prior to IMP injection.
- Administer IMP (aripiprazole IM depot 400 mg or aripiprazole 2M LAI 960 mg).

**Postdose:**

- Have subjects complete a VAS of the level of perceived pain at the injection site 1 hour ( $\pm$  15 minutes) postdose.
- Assessment of the injection site by the investigator completed approximately 1 hour ( $\pm$  15 minutes) postdose.
- Draw a PK blood sample at 4, 8, and 12 hours postdose.

**Days 176, 183, and 190  $\pm$  2 days (outpatient, subjects receiving aripiprazole 2M LAI 960 mg)**

- Document birth control methods.
- Record concomitant medications and review for prohibited or restricted medications.
- Record adjustment of current oral antipsychotic, mood stabilizer, or antidepressant therapy.
- Assess and record AEs.
- Take vital signs (systolic and diastolic blood pressure, heart rate, and body temperature).
- Administer the Since Last Visit version of the C-SSRS.

Protocol 031-201-00181

**Table 3.7.3-2 Sparse Sampling Schedule Trial Days and Activities**

|  |  |
|--|--|
| • Draw a PK blood sample between 8 AM and 2 PM.  | Day 197 ± 2 days (outpatient, all subjects) |
| • Document birth control methods.  |  |
| • Record concomitant medications and review for prohibited or restricted medications.  |  |
| • Record adjustment of current oral antipsychotic, mood stabilizer, or antidepressant therapy.                                       |  |
| • Assess and record AEs.   |  |
| • Perform a urine pregnancy test (FOCBP only).   |  |
| • Measure weight and calculate BMI.  |  |
| • Take vital signs (systolic and diastolic blood pressure, heart rate, and body temperature).  |  |
| • Administer the Since Last Visit version of the C-SSRS.   |  |
| • Assess EPS (SAS, AIMS, and BARS).  |  |
| • Administer the PANSS (schizophrenia subjects only).  |  |
| • Administer CGI-S scale and SWN-S (all subjects).   |  |
| • Administer the MADRS, YMRS, and CGI-BP (bipolar subjects only).  |  |
| Subjects who receive aripiprazole 2M LAI 960 mg only:   |  |
| • Draw a PK blood sample between 8 AM and 2 PM.  |  |
| Subjects who receive aripiprazole IM depot 400 mg only:   |  |
| Predose:  |  |
| • Assessment and confirmation by the investigator that the injection site is appropriate 30 minutes prior to IMP injection.          |  |
| • Have subjects complete a VAS of the level of perceived pain at the injection site approximately 30 minutes prior to IMP injection. |  |
| • Draw a PK blood sample within 2 hours prior to dosing.   |  |
| • Administer IMP.  |  |
| Postdose:   |  |
| • Have subjects complete a VAS of the level of perceived pain at the injection site 1 hour ( $\pm$ 15 minutes) postdose.             |  |
| • Assessment of the injection site by the investigator completed approximately 1-hour ( $\pm$ 15 minutes) postdose.                  |  |
| • Draw a PK blood sample 4, 8, and 12 hours postdose.  |  |
| Days 204, 211, and 218 ± 2 days (outpatient, all subjects)  |  |
| • Document birth control methods.  |  |
| • Record prior and concomitant medications and review for prohibited or restricted medications.                                      |  |
| • Record adjustment of current oral antipsychotic, mood stabilizer, or antidepressant therapy.                                       |  |

Protocol 031-201-00181

**Table 3.7.3-2 Sparse Sampling Schedule Trial Days and Activities**

- Assess and record AEs.
- Take vital signs (systolic and diastolic blood pressure, heart rate, and body temperature).
- Administer the Since Last Visit version of the C-SSRS.
- Draw a PK blood sample between 8 AM and 2 PM.

**Day 225/Early Termination  $\pm$  2 days (outpatient, all subjects)**

- Document birth control methods.
- Record concomitant medications and review for prohibited or restricted medications.
- Record adjustment of current oral antipsychotic, mood stabilizer, or antidepressant therapy.
- Assess and record AEs.
- Perform a urine pregnancy test (FOCBP only).
- Perform a physical examination.
- Measure weight.
- Take vital signs (systolic and diastolic blood pressure, heart rate, and body temperature).
- Administer a 12-lead safety ECG in triplicate (5 minutes apart).
- Collect hematology, clinical chemistry, and urinalysis clinical laboratory samples.
- Administer the Since Last Visit version of the C-SSRS.
- Assess EPS (SAS, AIMS, and BARS).
- Administer the PANSS (schizophrenia subjects only).
- Administer CGI-S scale and SWN-S (all subjects).
- Administer the MADRS, YMRS, and CGI-BP (bipolar subjects only).
- Draw a PK blood sample between 8 AM and 2 PM.

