## 2.2 Dosing Rationale

The extension of the dosing interval for the aripiprazole 2M LAI formulation is primarily through an increase in dose (ie, 960 mg). A recently completed single-dose trial evaluated administration of 780 mg or 1200 mg of aripiprazole to the gluteal muscle

Single-dose administration of 780 mg or 1200 mg aripiprazole LAI to the gluteal muscle resulted in, respectively, roughly a 200% and 300% higher aripiprazole  $C_{max}$  and exposure (AUC $_{\infty}$  and AUC $_t$ ) than previously observed following single-dose administration of 400 mg Abilify Maintena to the gluteal muscle (clinical study report [CSR] 31-11-290, Table 11.5.2.3.2.1-1). The mean  $t_{1/2}$  for aripiprazole following administration of 780 mg or 1200 mg aripiprazole 2M LAI to the gluteal muscle (22.1 days and 20.0 days, respectively) was comparable to the  $t_{1/2}$  following single-dose administration of 400 mg Abilify Maintena to the gluteal muscle. An interim model was fitted to observed PK data from [REDACTED] Based on simulations from the interim model, aripiprazole exposure is expected to be comparable or slightly higher after multiple-dose administration of aripiprazole 2M LAI 960 mg compared with 400 mg Abilify Maintena. Based on the simulations, the plasma steady-state of

Protocol 031-201-00181

aripiprazole is predicted to be reached by the fourth administration of aripiprazole 2M LAI 960 mg. Therefore, 4 administrations of aripiprazole 2M LAI 960 mg in the gluteal site were chosen for this trial. A total of 8 administrations of Abilify Maintena (aripiprazole IM depot 400 mg) were chosen to match the treatment duration of subjects receiving aripiprazole 2M LAI 960 mg.

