## 2.3 Trial Objectives

### 2.3.1 Primary Objectives

The primary objectives of this trial are:

- To determine the safety and tolerability of multiple-dose administrations of aripiprazole in adult subjects with schizophrenia or bipolar I disorder.
- To establish the similarity of aripiprazole concentrations on the last day of the dosing interval following the final administration of aripiprazole into the gluteal muscle site in adult subjects with schizophrenia or bipolar I disorder.
- To establish the similarity of aripiprazole exposure over the dosing interval following the administration of aripiprazole into the gluteal muscle site in adult subjects with schizophrenia or bipolar I disorder.

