### 3.2 Trial Treatments

#### 3.2.1 Investigational Medicinal Product

The test IMP (aripiprazole 2M LAI) administered in this trial will be supplied as aripiprazole IM depot 300 mg/mL RTU single-dose vials. The reference IMP will be aripiprazole IM depot 400 mg single-dose lyophilized vials. [REDACTED]

[REDACTED]

[REDACTED]

[REDACTED]

[REDACTED]

Subjects will be randomized (1:1) to receive multiple doses of:

- Aripiprazole 2M LAI 960 mg (test) - 2-month injection (total of 4 injections), administered every 56 days ( $\pm$  2 days) over the course of 32 weeks.
- Aripiprazole IM depot 400 mg (reference) - 1-month injection (total of 8 injections), administered every 28 days ( $\pm$  2 days) over the course of 32 weeks.

The IMP will be administered as a single injection in the gluteal muscle for a total of 4 (960 mg/injection) or 8 (400 mg/injection) injections. Due to possible safety and tolerability issues, a one-time dose reduction is allowed as outlined below:

- Aripiprazole 2M LAI 960 mg: a dose decrease to 660 mg. If the subject has had a decrease to 660 mg, a one-time increase back to 960 mg is then allowed.
- Aripiprazole IM depot 400 mg: a dose decrease to 300 mg. If the subject has had a decrease to 300 mg, a one-time increase back to 400 mg is then allowed.

Syringes and needles will be provided for the injection of IMP. Needles are selected based on the subject's body weight recorded on Day 1 and on each subsequent visit, as specified in [Table 3.2.1-1](#). Care must be taken to avoid inadvertent injection into a blood vessel, as per administration instructions. Detailed instructions on dose preparation and administration will be included in the site manual.

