| Serum hepatitis and HIV screen  | X                |                       |                |       |               |    |   |    |    |     |     |     |  |     |                   |
| Urine drug screen and urine or breath alcohol screen                              | X                | X                     |                |       |               |    |   |    |    |     |     |     |  |     |                   |
| Urine pregnancy test e   | X                | X                     |                | X     |               | X  | X   | X  | X  | X   |     | X   |  | X   |                   |
| FSH f  | X                |                       |                |       |               |    |   |    |    |     |     |     |  |     |                   |
| Hematology, clinical chemistry, and urinalysis                                    | X                | X                     |                | X     |               |    |   |    |    |     |     |     |  |     | X                 |
| Serum prolactin assessment  | X                | X                     |                | X     |               |    |   |    |    |     |     |     |  |     |                   |
| Physical examination  | X                | X                     | X
Day 15    | X     |               |    |   | X  |    |     |     |     |  |     | X                 |
| Weight  | X                | X                     |                | X     |               | X  | X   | X  | X  | X   |     | X   |  | X   |                   |

Protocol 031-201-00181

|   | Screening     | Check-in a | Days ± 2       |  |   |                  |  |                  |  |                  |  |  |                   |                |
|---|---------------|-----------------------|----------------|--|---|------------------|--|------------------|--|------------------|--|--|-------------------|----------------|
|   | Day -30 to -1 | Day 1                 | 8
15
22  | 29                                     | 36 b
43 b
50 b | 57               | 85                                     | 113              | 141                                    | 169              | 176 b
183 b
190 b | 197                                    | 204
211
218 | 225/
ET     |

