### 8.5 Clinical Laboratory

Clinical laboratory tests include serum chemistry, hematology, urinalyses and other lab analyses. Potentially clinically relevant laboratory test abnormalities will be listed by subject and by test. Criteria for potentially clinically relevant laboratory test abnormalities are provided in [Appendix 2](#). Subjects with aspartate aminotransferase (AST) or alanine aminotransferase (ALT)  $\geq$  3 x upper limit of normal value and total bilirubin  $\geq$  2 x upper limit of normal value will be listed. The incidences of potentially clinically relevant laboratory tests abnormalities based on observations during scheduled and unscheduled post-baseline visits will be tabulated by treatment formulation and disease type. Summary statistics for clinical laboratory measurements and changes from baseline will be presented by trial visit, treatment formulation and disease type.

If laboratory tests assessments are repeated for the same mapped trial visit, the last repeated values will be used for summary tables. This is accomplished by sorting patient data by visit date and visit time (if applicable) within the same trial visit. If the lab data are recorded as ranges (i.e., including < or > limit of quantification), these data are not

Protocol 031-201-00181

included in the calculations for changes from baseline but included in the calculations for incidences.

The incidence of prolactin level above the upper limit of normal range (potentially clinically relevant change) will be calculated by treatment formulation and disease type. Summary statistics (mean, standard deviation, median, minimum, and maximum) and changes from baseline in prolactin concentration will be presented by trial visit, treatment formulation and disease type. Similar analyses will be performed for male and female, respectively. Additionally, incidences of treatment-emergent relevant changes in lipid parameters and glucose (as defined in [Table 8.5-1](#)) will be summarized by treatment formulation and disease type, though those blood samples are not required to be collected at the fasted state.

Table 8.5-1 Criteria for Treatment-emergent Relevant Changes in Lipids Parameters and Glucose		
Parameters	Baseline	Any Post-baseline
Total Cholesterol (mg/dL)		
	Normal <200	High $\geq$ 240
	Borderline 200~<240	High $\geq$ 240
	Normal/Borderline <240	High $\geq$ 240
	Normal <200	Borderline/High $\geq$ 200
	Any Value	Increased $\geq$ 40
LDL Cholesterol (mg/dL)		

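### No prolactin sample is scheduled after Day 29, when each arm has had one trial injection, so the multiple-dose safety objective has no multiple-dose prolactin result

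*Protocol*

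**What the plan says.** The first primary objective (Protocol 2.3.1) reads "To determine the safety and tolerability of multiple-dose administrations of aripiprazole in adult subjects". Section 2.2 adds that the steady state of "aripiprazole is predicted to be reached by the fourth administration of aripiprazole 2M LAI 960 mg".

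In Protocol Tables 3.7-1 (sparse) and 3.7-2 (robust), the row "Serum prolactin assessment" is marked at screening, Day 1 and Day 29 and nowhere else. The day-by-day lists agree. The Day 29 entry in Tables 3.7.3-2 and 3.7.3-3 reads "Collect clinical laboratory samples for hematology, clinical chemistry, prolactin assessment, and urinalysis". The Day 225/Early Termination entry in both tables reads "Collect hematology, clinical chemistry, and urinalysis clinical laboratory samples".

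Dosing (Protocol 3.2.1) is "2-month injection (total of 4 injections), administered every 56 days" for the test product and "1-month injection (total of 8 injections), administered every 28 days" for the reference.

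SAP 8.5 plans the incidence of prolactin above ULN, and summary statistics in which "changes from baseline in prolactin concentration will be presented by trial visit, treatment formulation and disease type", with the same analyses for men and women separately. SAP Appendix 2 lists prolactin above ULN as potentially clinically relevant.

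**The concern.** The SAP gives prolactin its own paragraph of analyses, but the schedule supplies one post-baseline visit for them, and that visit comes before either regimen has been repeated. The final visit already draws blood for hematology and chemistry, yet prolactin is not on that line.

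Two things are at stake. First, a trial set up to describe multiple-dose safety would have no planned prolactin concentrations after repeated trial injections in either arm. Second, the planned tables could hide this. SAP section 8 defines incidence as subjects with at least one abnormality in the treatment phase, divided by the whole safety sample. Protocol 7.3 extends last observation carried forward to last-visit laboratory values. A value taken after one injection could therefore appear as the treatment-phase rate or the last-visit result.

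**Working it through.** The plan states no figure to reproduce here; the check is a count from the schedules.

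**1. Where prolactin is taken.** Both schedule tables and both day lists give screening, Day 1 predose and Day 29. Screening and Day 1 precede the first injection, so Day 29 (Week 4 in SAP Table 5.2-3) is the only post-baseline visit. The general chemistry line at Day 225/ET does not cover prolactin: it is absent from the legible serum chemistry panel in Protocol Table 3.7.6.2-1, and the other visits name it separately. Part of that table is redacted, but the timing comes from the schedules, which are legible.

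**2. Injections before each visit.** Dosing days are 1, 57, 113 and 169 (960 mg), and 1, 29, 57, 85, 113, 141, 169 and 197 (400 mg).

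| Visit | 960 mg | 400 mg |
|---|---|---|
| Day 29 | 1 | 1 |
| Day 57 | 1 | 2 |
| Day 113 | 2 | 4 |
| Day 169 | 3 | 6 |
| Day 197 | 4 | 7 |
| Day 225 | 4 | 8 |

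At Day 29 the 400 mg arm is due its second injection. The laboratory draw is not labelled predose, but both day lists place it ahead of the injection step. If it were taken afterwards, it would follow the second dose by hours at most.

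**3. What is left unobserved.** Injections on or after the last scheduled sample: 4 − 1 = 3 of 4 (960 mg) and 8 − 1 = 7 of 8 (400 mg). Day 29 is 28 days into the 224 days from Day 1 to Day 225: 28/224 = 12.5%. Steady state for 960 mg is predicted by the fourth dose, on Day 169, which is 140 days after the last scheduled sample (169 − 29).

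**4. Time since the previous antipsychotic.** Under Protocol 3.2.3, sparse subjects on a non-aripiprazole oral drug continue it for 7 days (960 mg) or 14 days (400 mg). Stopping at about Day 8 or Day 15 puts Day 29 about 29 − 8 = 21 or 29 − 15 = 14 days later. This applies to that subgroup only. Robust subjects switch to oral aripiprazole on Day 1 in both arms. Sparse subjects on oral aripiprazole have no different antipsychotic to clear. Sparse subjects on Abilify Maintena have no oral overlap.

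**5. With prolactin at Day 225.** The sample would follow 4 or 8 injections, 56 or 28 days after the last dose, which is the end of a dosing interval in both arms. On the enrolment range in Protocol 7.1, 100 to 170 completers would be expected to supply it.

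**The case against.** The strongest reply is that prolactin is a minor item. The primary safety endpoint names serum chemistry, hematology and urinalysis, and the synopsis lists prolactin under screening and other assessments. Safety is summarised descriptively, no steady-state prolactin comparison is promised, and SAP 8.5 can be run on one post-baseline visit. All of that stands. The gap lies in coverage of the objective and in SAP 8.5. It is neither a missing primary endpoint component nor a contradiction between the documents.

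Prolactin-related adverse events are also tabulated (SAP 8.10), and unscheduled laboratory tests are allowed (Protocol 3.7.6.2). These capture clinical consequences and individual follow-up, but not concentrations by arm for all subjects.

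Day 225 has weaknesses of its own. Subjects may resume a previous non-aripiprazole oral antipsychotic after Day 28 (Protocol 3.2.4), which Day 29 largely precedes and Day 225 does not. It also gives an end-of-interval value, not a peak. Both points stand and are reflected in the fix.

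A reader might infer two stronger points:

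- **Day 29 compares the arms at known, unequal fractions of steady state.** A simple accumulation formula assumes terminal decline by Day 28. Protocol 1.3 reports median times to peak of 25.1 days (780 mg) and 41.0 days (1200 mg), with a secondary peak. The documents give no time to peak for 400 mg and no relation between aripiprazole concentration and prolactin.
- **Washout of the previous drug is unequal across the whole trial.** It holds only for the sparse subgroup in step 4 of the working, whose size is not given.

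**Conclusion.** The point holds as a gap in the schedule with a cheap remedy. No subject, of up to 258, has a scheduled prolactin value after multiple trial injections, and 3 of 4 or 7 of 8 injections come on or after the last sample. This rests on the scheduled visits alone, on the Day 29 draw being taken in the listed order, and on counting trial injections: sparse subjects who entered on Abilify Maintena may carry earlier 400 mg doses, but that supplies no multiple-dose 960 mg data.

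Reporting Day 29 as a last-visit result is a possibility, not a certainty. Protocol 7.3 applies the carry-forward rule to laboratory values, whereas SAP 5.3 mentions only the EPS and efficacy scales. Nor can a last-visit value simply be called multiple-dose, because SAP 5.1 includes early termination in its definition of last visit. The primary PK analyses are not affected.

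**What to change.** 1. Add prolactin to the Day 225/ET laboratory line in Protocol Tables 3.7-1, 3.7-2, 3.7.3-2 and 3.7.3-3, using the existing blood draw.
2. In SAP 8.5, report Day 225 completers (4 or 8 injections) as the multiple-dose, end-of-interval prolactin result. Use the SAP 7.1 definition of completer, which is Day 225 in both arms; Protocol 3.10 puts completion at Day 197 for 400 mg.
3. Report early-termination values separately, by number of injections received.
4. Flag subjects who resumed a non-aripiprazole antipsychotic after Day 28.
5. Label Day 29 as after the first trial injection. If the schedule can no longer be changed, do at least this, and do not present Day 29 as a last-visit or whole-treatment result.

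The cost is one extra assay per subject and a minor schedule amendment, with no new visit. That the assay fits the blood already drawn is an assumption to confirm with the laboratory, since the documents give no tube or volume requirements. Day 225 will not show peak prolactin.
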